6.5.2.2 Time to Response

The TTR is defined as the elapsed time from the date of the first study drug dose until the date of first documented confirmed CR or PR, whichever occurs first. Summary statistics of TTR for subjects with confirmed CR or PR (objective response) will be presented.

TTR will also be summarized by treatment cycles completed when the first documented response occurred.

TTR for subjects with confirmed CR or PR will be analyzed using KM method. The median and quartiles of TTR from KM estimation will be provided with 2-sided 95% CIs if estimable. The cumulative probabilities will be plotted over time.

6.5.2.3 ORR Using Prince (2010)²

The ORR is the proportion of subjects achieving a BOR of confirmed CR+CCR or PR per Prince (2010)² criteria. The Primary Efficacy Analysis Set will be used for analysis. See [Section 6.4.3](#) for the derivation of BOR.

The 2-sided, exact 95% CI of ORR will be calculated using the Clopper-Pearson method.

6.5.2.4 Skin Response (according to mSWAT)

ORR for skin response based on the mSWAT score, is defined as the proportion of subjects with best skin response of CR or PR. See [Section 6.4.2](#) for the derivation of the BOR for skin response.

The 2-sided, exact 95% CI of ORR will be calculated using the Clopper-Pearson method.

In addition, waterfall plot presenting each subject's percentage change in mSWAT from baseline at postbaseline nadir before data cutoff will be provided.

6.5.2.5 Duration of Skin Response

The duration of skin response based on the mSWAT score is defined as time from the date when criteria for confirmed skin response (CR or PR) was first met until the date of documented PD or death due to any cause for those subjects with a confirmed PR or CR. For subjects who did not experience PD or death by the end of data cut off, censoring rules for duration of skin response are the same as those of PFS.

Duration of skin response will be analyzed following the same approach in [Section 6.5.2.1](#).

6.5.2.6 Time to Skin Response

The time to skin response based on the mSWAT score is defined as time from the date of first dosing to the date when criteria for confirmed skin response (CR or PR) are first met.

Time to skin response will be analyzed following the same approach in [Section 6.5.2.2](#).

6.5.3 Other Efficacy Analyses

6.5.3.1 Exploratory Efficacy Analyses

PROGRESSION FREE SURVIVAL

The PFS is defined as the date of first dosing to the date of documented PD or death as a result of any cause (whichever occurs first).

PFS will be analyzed for the Primary Efficacy Analysis Set and Full Analysis Set.

PFS will be analyzed using KM method. The median, quartiles and the PFS rates at 3, 6, 9, 12 months and so on (depending on data adequacy) will be calculated using KM method and

presented with 2-sided 95% CIs if estimable. The cumulative probabilities of PFS will be plotted over time.

The PFS censoring rules in this SAP and definition of progression date will follow the Food and Drug Administration (FDA) “Guidance for Industry Clinical Trial Endpoints for the Approval of Cancer Drugs and Biologics (2007)”

Table 2 Censoring Rules for Analysis of Progression-Free Survival

No.	Situation	Date of Event (Progression/Death) or Censoring	Outcome
1	No baseline tumor or postbaseline GRS assessments	Date of first dose	Censored
2	Progression documented between scheduled visits*	Date of PD by GRS assessment	Event
3	No progression at the time of data cutoff	Date of last adequate GRS assessment prior to or on date of data cutoff	Censored
4	New anticancer treatment started	Date of last adequate GRS assessment prior to or on date of new anticancer treatment	Censored
5	Death before first PD by GRS assessment	Date of death	Event
6	Death between adequate GRS assessment visits**	Date of death	Event
7	Death or progression after more than one missed visit/GRS assessment***	Date of last adequate GRS assessment before missed GRS assessments	Censored

CR = complete response, PD = progressive disease, PR = partial response, SD = stable disease.

Any GRS assessments after new anticancer treatment starts will not be considered in the definition of PFS.

*If subject is not treated beyond initial PD, date of PD should be used. If subject is treated beyond initial PD (per protocol), date of initial PD should be used if consecutive PDs; if there are intervening SD/PR/CR between two PDs, date of the later PD should be used. ** Adequate GRS assessment is assessment of CR, PR, SD and PD at regular interval.

***More than one missed visits is defined as having the duration between the last tumor assessment and death or PD longer than 44 days which is $(3) \times 2 \times 7 + 3 - 1$ days for subjects on every 3 weeks (-3 days window) for subjects on every 3 weeks tumor assessment schedule during treatment; after date of end of treatment date, 69 days which is $(4+1) \times 2 \times 7 - 1$ days for subjects on every 4 weeks (± 1 week) for 1 year after end of study treatment; 209 days which is $(12+3) \times 2 \times 7 - 1$ days for subjects on every 12 weeks (± 3 weeks) tumor assessment schedule from 1 year after end of study treatment up to 3 years.

The priority of the censoring rules is as follows:

1. If the subject had PD or death, the following sequence will be applied:
 - If a subject did not have a baseline tumor assessment (No. 1), the subject will be censored on the date of first dose. However, if the subject died within 41 days (6 weeks-1day) after first dose and did not receive a new anticancer treatment, it will be

- counted as PFS event at the date of death. If a subject had new anticancer treatment before PD or death (No. 4), the subject will be censored on the date of the last adequate GRS assessment prior to or on the date of new anticancer treatment.
- If a subject missed two or more tumor assessments before PD or death (No. 7), the subject will be censored on the date of the last adequate GRS assessment before PD or death. Note that if a subject is censored by both this criterion and the anticancer treatment criterion, the earliest censoring date will be used.
 - Otherwise, if a subject had an event (No. 2, No. 5, or No. 6), the earliest event date will be used.
2. If a subject did not have PD or death, the censoring date will be the earliest censoring date if the subject met multiple censoring criteria (No. 1, No. 3, No. 4, No. 7).

TIME TO PROGRESSION (TTP)

TTP is defined as the time from the date of first dosing to the date of documented PD or death as a result of CTCL. The same censoring rules, except for death (other cause), as in the analysis of PFS will be applied in calculation of TTP.

TTP will be analyzed following the same approach as for PFS in [Section 6.5.3.1](#).

CLINICAL BENEFIT RATE (CBR)

The CBR is defined as the proportion of subjects who had best overall response of CR or PR or Durable SD by IRC or investigator assessment.

Durable Stable disease must be achieved at ≥ 23 weeks after first dose of study drug to be considered best overall response based on Olsen (2011)¹ criteria.

The 2-sided, exact 95% CI of CBR will be calculated using the Clopper-Pearson method.

PRURITUS IMPROVEMENT

Subjects will rate the severity of pruritus using a 100-mm visual analog scale (VAS), on which zero indicates no itch and 100 indicates worst possible itch. A clinically significant improvement is defined as an absolute decrease of 20 mm from baseline maintained for ≥ 4 weeks; baseline score must be ≥ 20 . Subject's pruritus improvement rate is defined as the proportion of subjects with a clinically significant improvement in pruritus. The 2-sided, exact 95% CI of pruritus improvement rate will be calculated using the Clopper-Pearson method.

In addition, the percentages of subjects who have $\geq 20\%$ and $\geq 50\%$ improvements (decreases) relative to baseline will be tabulated.

SENSITIVITY ANALYSES

Sensitivity analyses for ORR in subjects receiving versus subjects not receiving steroid medication for any cycle during the study will be performed. ORR (the proportion of

subjects achieving a BOR of confirmed CR or PR) will be summarized along with the 2-sided, exact 95% CI, using the Clopper-Pearson method.

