### Efficacy Assessments:

The ISCL/EORTC response criteria for mycosis fungoides and Sezary syndrome (Olsen 2011) will be used for efficacy analysis in the Lead-In as well as for primary efficacy analysis in the Main Study.

Tumor responses will be assessed by an independent central Response Review Committee (IRC) (Imaging Core Laboratory) for primary efficacy analysis in the Main Study. Tumor responses will also be assessed by the site investigator, and these site assessments will be used to make subject treatment decisions.

The response criteria described in Prince (2010) will be used as a supplemental alternate method (SAM) for the secondary objective of ORR. This supplemental assessment will be conducted by the IRC only.

For both the Lead-In and Main Study, photographs and CT scans will be sent by the investigator site to an Independent Imaging Core Laboratory designated by the sponsor for analysis. Laboratory results, including blood, as well as investigator skin assessments as entered in the CRF, will be sent to the Core Laboratory by the sponsor. At the time of data cutoff for primary analysis of the Main Study, the sponsor may choose to discontinue sending data (including photographs and scans) to the Imaging Core Laboratory.

Tumor assessment schedule (see protocol body for details):

- At screening, skin, lymph node assessment by palpation, blood assessment, and CT scan for assessment of nodal and visceral disease.
- During treatment: (1) skin and blood disease assessment, on Day 1 of every cycle, (2) lymph node assessment by palpation and CT scans of nodal disease (as needed) and visceral disease (as needed), and (3) lymph node biopsy is only recommended in situations where the histology would affect the Global

Response score. End-of-treatment tumor assessments should be performed if required for Global Response Score determination.

Follow-up: (1) skin and blood disease assessment to be performed every 4 weeks for 1 year after end of study treatment, then every 12 weeks thereafter for up to 3 years, or sooner if clinically indicated, (2) other assessments e.g. lymph node palpation, CT scans of nodal and visceral disease, or lymph node biopsy only if appropriate, as described in [Section 9.5.2.2](#) of the protocol.

Measurement of Tumor Burden (see protocol body for details)

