### Main Study:

All of the efficacy analyses for tumor assessment related endpoints will be performed using independent central review data as primary analyses. In addition, similar analyses will be performed using investigator assessment data as the secondary analyses.

All efficacy and Quality of Life (QoL) analyses will be performed primarily in Stage I – III Main Study subjects plus the Stage I – III Lead-In subjects from the 9  $\mu\text{g}/\text{kg}/\text{day}$  dose group combined, and additionally in all subjects from the Main Study.

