##### Treatment Phase

The Treatment Phase will consist of the following Periods:

- **Treatment Period.** Treatment with E7777 for up to 8 cycles. Each cycle of 21 days is one Period. Subjects who have attained skin tumor response and are deriving clinical benefit from E7777 treatment may continue receiving treatment beyond eight cycles, at the discretion of the treating physician.
- **Follow-up Period.** Tumor assessment until discontinuation of treatment due to progressive disease [PD]); immunogenicity, and survival follow-up until relapse or initiation of new systemic anti-cancer therapy. All Follow-up assessments performed for up to 3 years after end of treatment, or until sponsor termination of the study.

After data cutoff for the primary analysis in the Main Study, the study moves to the Extension Phase.

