### 9.3.3 Removal of Subjects From Therapy or Assessment

The investigator may discontinue treating a subject with study treatment or withdraw the subject from the study at any time for safety or administrative reasons. The subject may decide to discontinue study treatment or withdraw from the study at any time for any reason; however, the subject should remain on study, if possible, for follow-up.

If a subject discontinues early from study treatment, the subject will enter the Follow-Up Period and complete protocol-specified off-treatment visits, procedures, and survival follow-up unless the subject withdraws consent.

During the Lead-In part, subjects who are not evaluable for DLT in Cycle 1 should be replaced. In the Main Study, subjects who withdraw from treatment or study participation will not be replaced. Treatment will stop upon disease progression, unacceptable toxicity, or death.

During the Follow-Up Period, subjects who have discontinued study treatment without progression should have disease assessments as specified in [Section 9.5.2.2](#) until disease progression is documented or another new systemic anti-cancer therapy is initiated.

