## 9.5.2 Efficacy Assessments

### 9.5.2.1 Overview

#### Primary Method for Tumor Assessment (Site review plus Independent Central review)

The ISCL/EORTC response criteria (Olsen 2011) will be used as the primary method for efficacy analysis. This method will be used by both the Site investigator and the Independent Review Committee (IRC).

The dataset from the Stage I – III Main Study subjects plus the Stage I – III Lead-In subjects from the 9µg/kg/day dose group combined as generated by the IRC will be the primary efficacy analysis dataset. All subjects from the Main Study will be assessed for efficacy by the IRC.

For both the Lead-In and the Main Study, the site will report on the CRF their local/investigator tumor response assessment; site assessments will be used to make subject treatment decisions.

Tumor assessment methods and schedules are provided in [Section 9.5.2.3](#).

Tumor burden scoring and the ISCL/EORTC response criteria are described in [Appendix 1](#).

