CT/F-DG-PET-CT scans of skin disease may be performed as necessary for response assessment if the CT acquisition is of diagnostic quality.

- n: Adverse events will be assessed at every visit, until 30 days after the last treatment dose.
- o: Survival follow-up performed every 3 months after discontinuation from study treatment, up to 3 years from end of study treatment.
- p: QoL is to be performed at Baseline, on Day 1 of every cycle during Treatment, at EOT, and during every Tumor Assessment visit during Extension. The QoL will be assessed in Stage I – III Main Study subjects plus the Stage I – III Lead-In subjects from the 9μg/kg/day dose group combined.
- q: Follow-up tumor assessments (except in subjects who discontinued treatment due to PD), immunogenicity and survival follow-up until relapse, or initiation of new systemic anti-cancer therapy, for up to 3 years after EOT.

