### **Follow-up Period:**

Tumor assessments should be performed until PD. Immunogenicity and survival assessments should be performed until discontinuation from study. All assessments for up to 3 years from EOT. Refer to the Schedule of Assessments, [Table 4](#), for a description and the schedule for all other Follow-Up assessments.

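### Site-assessed PD ends tumour assessments while DOR and PFS run on IRC PD, so a site-only progression is censored and IRC durations may be overstated by an unknown amount

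*SAP*

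**What the plan says.** **Who decides.** Protocol 9.5.2.1 gives treatment decisions to the site: "site assessments will be used to make subject treatment decisions".

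**When assessments end.** Protocol 9.1.4 sets the Follow-up Period as "Tumor assessment until discontinuation of treatment due to progressive disease". Protocol 9.3.3 provides for continued assessment in a narrower group: "subjects who have discontinued study treatment without progression should have disease assessments". Footnote q of Table 4 carries the matching exemption for those who stopped for PD. Protocol 9.5.5.2 says "Tumor assessments should be performed until PD" and does not name the reader. Nothing in the documents makes IRC confirmation a condition for ending assessments.

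**Whose PD is analysed.** The Protocol Synopsis (Statistical Methods, Main Study) states: "All of the efficacy analyses for tumor assessment related endpoints will be performed using independent central review data as primary analyses". SAP 6.1 likewise uses IRC responses for the primary endpoint and the associated secondary and exploratory endpoints. Investigator-based versions are also reported.

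**How subjects without IRC PD are handled.** SAP 6.5.2.1 gives DOR the PFS censoring rules, and SAP 6.5.3.1 gives them to TTP with an exception for deaths from other causes. In Table 2, row 3 (no progression at cutoff) censors at "Date of last adequate GRS assessment prior to or on date of data cutoff". Row 4 censors at the last adequate assessment up to the start of new anticancer treatment. Row 7 censors a death or PD that follows more than one missed assessment. No row covers a site PD that the IRC does not call.

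**The concern.** The reader whose call ends observation is not the reader whose call counts as the event. When the two disagree on the treatment-ending PD, the IRC has no later visits on which to reach PD, and the subject enters the Kaplan-Meier estimate as progression-free and censored.

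Kaplan-Meier treats a censored subject as having the same future hazard as those still under observation. A subject who left assessment because an investigator, using the same response criteria, judged the disease to be progressing probably has a higher hazard. The estimated median and the 6- and 12-month probabilities would then rise with disagreement between readers rather than with drug effect. DOR is the first secondary endpoint listed in a single-arm study meant to support a marketing application, so its reading matters even though no test depends on it.

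**Working it through.** **1. Tracing one subject.** Take an IRC responder whose treatment stops for a site PD that the IRC scores as non-PD.

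- No new therapy by cutoff: row 3 applies, censored at the last adequate GRS assessment.
- New anticancer therapy: row 4 applies, censored at the last adequate assessment up to that start.
- Later death without new therapy: an event if it falls within the row 7 gap, otherwise censored. The row 7 footnote measures the gap from the last tumour assessment to death, so it applies even though no further visit was due.

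**2. The row 7 gaps reproduce.**

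- On treatment: 3 × 2 × 7 + 3 - 1 = 44 days
- First year after treatment: (4 + 1) × 2 × 7 - 1 = 69 days
- Thereafter: (12 + 3) × 2 × 7 - 1 = 209 days

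For a subject whose assessments ended with treatment, the 44- or 69-day gap is the relevant one.

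**3. Size of the effect.** The documents give no discordance rate and no expected DOR. Everything below is an assumption: exponential time to IRC PD with hazard λ, and a share d of progressions called by the site only.

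*Upper limit.* Each site-only PD coincides with what would have been an IRC event. The estimated hazard is (1-d)λ, so the median ratio is 1/(1-d):

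- d = 10%: 1/0.90 = 1.11
- d = 20%: 1/0.80 = 1.25
- d = 30%: 1/0.70 = 1.43

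*Lower end.* Site-only PD occurs independently of IRC progression. Censoring is then non-informative and the ratio is 1.0.

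*In between.* A large-sample simulation (400,000 subjects) with a true IRC median of 9 months, in which site-only PD comes one 21-day visit before IRC PD would be met:

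| d | Median under SAP rule (months) | Ratio to 9 | 12-month probability (true 40%) | Median with site PD as event (months) |
|---|---|---|---|---|
| 10% | 9.9 | 1.10 | 43% | 8.9 |
| 20% | 11.1 | 1.23 | 47% | 8.9 |
| 30% | 12.6 | 1.40 | 52% | 8.8 |

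With independent site PD, the simulated median under the SAP rule stays at 9.0 months for every d.

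**4. What the supportive analysis would show.** When site PD closely precedes IRC PD, counting it as an event errs slightly low (last column). When site PD is independent of IRC PD, it errs lower. Site-only PD then adds a hazard of λd/(1-d), the total is λ/(1-d), and the median becomes 9 × (1-d) = 8.1, 7.2 and 6.3 months. In both scenarios the IRC result and the supportive result lie on either side of the true value or meet it.

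**The case against.** The strongest case against is that disagreement may be rare and is already visible.

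- Assessment does not always stop at the first site PD. Protocol 9.4.1 lets treatment continue when the investigator wants PD confirmed, and then ends it only after two successive PD notations. Appendix 4 Table 5 note 2 asks for doubtful PD to be confirmed after at least 4 weeks. Doubtful calls, where readers are most likely to differ, are thus the ones most likely to stay under observation.
- The IRC works largely from the same data. Protocol 9.5.2.1 sends it the site's skin assessments and the laboratory results including blood, and flow cytometry is central. Skin PD is largely a numerical mSWAT rule.
- Investigator-assessed endpoints, swimmer plots and reasons for discontinuation are all to be reported.
- DOR is secondary, PFS and TTP are exploratory, and none has a threshold.

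Most of this stands as a limit on size. It does not close the gap. A PD that ends treatment after two notations is more likely to be real, so censoring it is more likely to be informative. The data shared with the IRC may keep discordance low, but the plan neither measures it nor bounds its effect. Investigator DOR has its own responders and response dates, so a difference from IRC DOR mixes disagreement about response with disagreement about progression. The only sensitivity analysis named in SAP 6.5.3.1 concerns ORR by steroid use.

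**Conclusion.** The gap is real. Under the plan as written, a treatment-ending PD called only by the site becomes a censored observation in the main DOR, PFS and TTP analyses, at a moment that is plausibly informative. These estimates may therefore be overstated. The median ratio lies between 1.0 and 1/(1-d), given an exponential model and an assumed d; the true d is unknown.

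Four stronger readings are tempting, and the documents do not support them:

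- *Every site PD ends assessment at once.* Treatment and assessment may continue past a first PD.
- *IRC duration is overstated, by 1/(1-d).* The direction is an expectation, the factor is a limiting case, and the bias is zero if site PD carries no information on IRC PD.
- *Duration of skin response is affected to the same degree.* It uses the same censoring rules, but its response rests on mSWAT scores that the site investigator makes and the IRC receives. An equal effect has not been shown.
- *The primary conclusion is at risk.* ORR does not use this censoring rule.

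**What to change.** Keep the IRC analysis as the main one. Add to SAP 6.5.2.1 and 6.5.3.1 a supportive analysis, in IRC responders for DOR and in the Primary Efficacy Analysis Set for PFS, whose event is the earliest of IRC PD, site PD that ended tumour assessments, or death. Beside it, report the number of subjects censored in the IRC analysis after a site-only PD. If that number is near zero, the matter is settled; if not, the two curves show how much depends on it.

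The cost is one extra derivation and table, from site and IRC assessments already collected. No visit or procedure changes. The supportive estimate is conservative and may be shorter than the IRC result. It should be labelled as a supportive bound, not as a corrected estimate.

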#### 9.4.1.5 Dose Interruption or Modification

##### **Dose Delays**

- Dose delays will be allowed for toxicities. Resumption of dosing will be according to the guidelines provided in [Table 1](#).
- The maximum delay is 21 days before the day the next course is scheduled to start.
  - A full dose will be given if toxicities are resolved within this 21-day period.
  - A dose delay lasting > 21 days will lead to permanent discontinuation of treatment.
  - If a cycle is not delivered in full, regardless of the reason, the missing doses will not be replaced and the cycle will be considered as complete. The missing doses will be captured per dose intensity calculations.
- Two consecutive dose delays due to toxicity will lead to a permanent dose reduction by 50% without possible reescalation.
  - Only one dose reduction to 50% will be allowed, regardless of the reason. The requirement for additional dose reductions, as defined previously, will lead to permanent discontinuation of treatment.
- The starting date of a new cycle will coincide with the date of treatment resumption following a dose delay or dose reduction.
- Dose delays are also allowed for scheduling purposes and if in the subject's best interest in the opinion of the investigator. The maximum delay for this is 42 days.

Study drug interruption and dose reduction instructions for subjects who experience an E7777-related toxicity are presented in [Table 1](#).

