#### **1. Skin Disease Assessment**

Skin tumor burden will be quantified using a modified Severity Weighted Assessment Tool (mSWAT) that provides an mSWAT score. The mSWAT score measures the body surface area (BSA) involved in skin disease with a weighting factor applied according to the severity of the type of skin lesion, which can be patch, plaque, or tumor. The mSWAT

can be utilized to track erythroderma by the summation of BSA involved with patch disease (macular erythema) and plaque disease (erythema with induration/edema). In addition, subject(s) should be evaluated for the appearance of new skin tumor lesion(s) at each time point after the initiation of treatment. A sample of the worksheet for calculating the mSWAT score is provided in [Appendix 4](#). Note: The worksheet for use at the site will be provided separately to each site.

*Supplemental Assessment Method (SAM) using Prince (2010) Criteria (only for subjects with skin lesions comprising < 10% of BSA)*

Since the IRC will perform a secondary analysis based upon the method of [Prince \(2010\)](#), a supplemental measurement will be made by the site investigator at the time of mSWAT assessment, for subjects with skin lesions comprising < 10% of BSA. The investigator will identify, photograph, and measure up to five representative skin lesions (generally the largest and most representative of different locations, such as chest, abdomen, leg, arm, head, neck, if applicable; measurements will be of two-dimensional perpendicular diameters). These measurements will be collected on the eCRF and will be used only by the IRC. These lesions (even if they have disappeared) should be evaluated and photographed at all mSWAT assessment time points. A sample of the worksheet for collecting skin lesion data per supplemental assessment method (by Prince 2010) is shown in [Appendix 4](#). Note: The worksheet for use at the site will be provided separately to each site.

The assessment schedule is as follows:

- a. At Screening, assessment to determine study eligibility
- b. During treatment
  - Day 1 (-3 days) of every treatment cycle (minus 3-day window allowed)
- c. At EOT, if required for Global Response Score determination
- d. During Follow-up: every 4 weeks ( $\pm$  1 week) for 1 year after end of study treatment, then every 12 weeks ( $\pm$  3 weeks) thereafter for up to 3 years, or sooner if clinically indicated

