### 3. Blood Disease Assessment

Blood tumor burden will be assessed by quantifying CD4+CD26 cells by flow cytometry; CD4+CD7 cells may be used in CD26+ subjects.

Assessment frequency

- a. At Screening
- b. During treatment
  - i. Day 1 (-3 days) of every treatment cycle
- c. At EOT, if required for Global Response Score determination
- d. During Follow-up: Every 4 weeks (± 1 week) for 1 year after end of study treatment, then every 12 weeks (± 3 weeks) thereafter for up to 3 years, or sooner if clinically indicated.

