6.5.2 Secondary Efficacy Analyses

6.5.2.1 Duration of Response

The DOR is defined as the time from the date that a confirmed objective response (CR or PR) was first met until the date of documented PD or death due to any cause for those subjects with a confirmed PR or CR. For subjects who did not experience PD or death by the end of data cut off, censoring rules for DOR are the same as those of PFS.

- Duration of objective response (months) = (Date of PD/Death or Censor Date – Date of first objective response + 1) × 12/365.25, for subjects with objective response.

For subjects with confirmed PR or CR, the DOR will be analyzed using Kaplan-Meier (KM) product-limit estimates. Probabilities of DOR ≥ 6 and 12 months will be presented with 2-sided 95% CIs as appropriate, if they can be estimated from the model. The median and quartiles of DOR from KM estimation will be provided with 95% CIs if estimable. The DOR curve from KM method will be provided.

For subjects with confirmed PR or CR, the number and percentage of subjects with DOR ≥ 6 and 12 months will also be summarized as descriptive statistics as appropriate.

The swimmer plot will be plotted demonstrating the treatment duration and timepoint responses over time.

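### The SAP's 44-day on-treatment missed-visit limit is shorter than assessment gaps the protocol allows, so a PD found on schedule after a long scheduling delay is censored

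*SAP*

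**What the plan says.** **SAP, section 6.5.3.1.** Rule 7 of Table 2 covers "Death or progression after more than one missed visit/GRS assessment" and censors at the last adequate GRS assessment before the missed ones. The footnote turns this into a day count: "More than one missed visits is defined as having the duration between the last tumor assessment and death or PD longer than 44 days". The 44 days come from two 21-day intervals plus a 3-day window, minus one. The priority list below the table states the condition as a visit count: "If a subject missed two or more tumor assessments before PD or death (No. 7". Neither the table, its footnotes nor the priority list makes an exception for dose delays.

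**Protocol, section 9.5.2.2.** Skin is assessed on "Day 1 (-3 days) of every treatment cycle (minus 3-day window allowed", and blood on "Day 1 (-3 days) of every treatment cycle". SAP section 6.4.1 dates each GRS by the mSWAT assessment, so the skin date determines the gap.

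**Protocol, section 9.4.1.5 (Dose Delays).** "The starting date of a new cycle will coincide with the date of treatment resumption following a dose delay or dose reduction". Delays for toxicity may last up to 21 days; beyond that, treatment stops permanently. Delays for scheduling or the subject's best interest have their own limit: "The maximum delay for this is 42 days". No tumor assessment is scheduled during a delay.

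**Reach of the rule.** In SAP section 6.5.2.1, "censoring rules for DOR are the same as those of PFS". Section 6.5.2.5 says the same for duration of skin response. TTP uses the PFS rules except for deaths from other causes.

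**The concern.** The 44-day limit assumes that on-treatment assessments come every 21 calendar days. In this protocol they follow the cycle, and the cycle moves when dosing is delayed. A subject can attend every required assessment and still have more than 44 days between two of them. If the second one shows PD, the SAP treats the subject as having missed more than one visit, discards the event, and censors at the previous assessment.

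The test also depends on the outcome. As worded, it looks only at the gap immediately before PD or death. A subject who is stable after the same long gap, and progresses later at a normally spaced visit, keeps the full follow-up and the event. Only the subject who progressed across the gap loses it. That tends to push Kaplan-Meier curves up.

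The endpoints at stake are exploratory PFS and TTP and, more visibly, DOR and duration of skin response. Those two are secondary, and their analyses include estimated probabilities at 6 and 12 months.

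**Working it through.** **Inputs.** Cycle length is 21 days (protocol 9.1.4). The assessment window is -3 days (9.5.2.2). The cycle-start window is plus or minus 1 day from Cycle 3 (Table 4, footnote j). The maximum delay is 21 days for toxicity and 42 days for scheduling or best interest (9.4.1.5).

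**The SAP's own limits reproduce.** On treatment: 3 × 2 × 7 + 3 - 1 = 44. Follow-up: (4 + 1) × 2 × 7 - 1 = 69 and (12 + 3) × 2 × 7 - 1 = 209.

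**Gap between consecutive on-schedule assessments** = 21 + delay + w. Here w is 0 if both fall on Day 1, +3 if the earlier one was 3 days early, +4 if the cycle also started one day late, and -3 if only the later one was 3 days early. An event is censored if the gap exceeds 44.

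| Situation | Visits missed | Gap (days) | Rule 7 result |
|---|---|---|---|
| No delay, both on Day 1 | 0 | 21 | event |
| Toxicity delay 21, both on Day 1 | 0 | 21 + 21 = 42 | event |
| Toxicity delay 21, w = +3 | 0 | 45 | censored |
| Toxicity delay 21, w = +4 | 0 | 46 | censored |
| Scheduling delay 42, w = -3 | 0 | 60 | censored |
| Scheduling delay 42, both on Day 1 | 0 | 21 + 42 = 63 | censored |
| Scheduling delay 42, w = +3 | 0 | 66 | censored |
| Scheduling delay 42, w = +4 | 0 | 67 | censored |
| No delay, earlier visit at -3 days, PD on Day 1 | 1 | 42 + 3 = 45 | censored |

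**Shortest delay that triggers censoring.** This needs 21 + delay + w > 44, so delay > 23 - w. The result is 24 days for w = 0, 21 for w = +3, 20 for w = +4 and 27 for w = -3.

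**The one-missed-visit row.** The largest undelayed gap with one missed visit, counting the -3-day window, is 45 days. The SAP subtracts 1 to get 44 and then censors anything longer than 44, so it catches the 45-day case. That contradicts the priority list, which requires two or more missed assessments. The follow-up limits have the same one-day slip when both windows are used in full: 56 + 7 + 7 = 70 against 69, and 168 + 21 + 21 = 210 against 209.

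**Censoring date.** Table 2 censors before the missed assessments. If none was missed, that date is undefined. The priority list's version (last adequate assessment before PD or death) still yields a date, and that date discards an event found on schedule.

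**The case against.** **A day limit is a legitimate convention.** It caps how long disease status may go unobserved, whatever the reason. Dating a PD at its detection after a 66-day gap also lengthens PFS. The SAP says its censoring follows a regulatory guidance, which was not available to check. This stands as a reason to keep the day-count analysis as a sensitivity analysis. It does not rescue the primary rule, because the SAP describes its criterion as missed assessments, and here none need have been missed.

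**Toxicity.** A reader might infer that the rule mainly removes events from subjects who tolerate treatment badly, which would make the censoring clearly informative. The documents do not support that. A full 21-day toxicity delay gives 42 days and the event is kept; it crosses the limit only by a day or two, with the windows at their extreme. The delays that matter are those for scheduling or best interest, and nothing shows that these are prognostic.

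**Size.** A reader might put a percentage on the inflation of the medians. That needs an assumed share of long gaps, which the documents do not give. It also must not apply an on-treatment share of PDs to the whole curve, because follow-up visits are timed from end of treatment and dose delays do not move them.

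**End of treatment.** One might argue that a single missed follow-up visit already breaches the 69-day limit: 21 + 28 + 28 = 77 days from the last Day 1. That assumes treatment ends 21 days after Day 1. Counted from the Day 5 dose it is 4 + 56 = 60 days, within the limit. The example is not secure.

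**Reading of the 42 days.** If this were the whole Day 1-to-Day 1 interval, the gap would be 42 days, or 45 with the -3-day window, and the excess would be one day. The plain reading is a delay of 42 days.

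**Conclusion.** The conflict is real but bounded. With no assessment missed, the protocol permits on-treatment gaps of 63 days (66 to 67 with windows), 19 to 23 days beyond the SAP's limit. A PD found after a delay of about 24 to 42 days is therefore censored. A smaller fault exists without any delay: one missed visit can produce a 45-day gap and be treated as more than one.

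PFS, TTP, DOR and duration of skin response are affected, and the tendency is towards longer Kaplan-Meier estimates. ORR, the only endpoint with a success criterion, is not affected. The number of events lost and the size of the bias cannot be computed without the frequency of delays.

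The conclusion assumes that 42 days is the length of the delay, and that no extra assessment is made during it; one would shorten the gap. No position is taken on how long delays should be. The point is that the censoring rule and the protocol schedule must be reconciled.

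**What to change.** Replace the day count in the footnote with a visit count. Apply rule 7 only when two or more scheduled assessments were actually missed before PD or death, counted against each subject's actual cycle Day 1 dates and follow-up visit dates, including the interval that spans end of treatment. Otherwise count PD or death as an event on its documented date. State how end of treatment is dated for this purpose. Use the same rule for TTP, DOR and duration of skin response, and report the present fixed-day rule as a sensitivity analysis.

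Adding documented delay days to 44 may look like a simpler route, but it is not equivalent. With no delay, the 45-day gap with one missed visit would still be censored.

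The cost is a revised SAP footnote and some programming. The dosing dates needed are already collected, since SAP section 6.7.1 plans listings of all dosing records. Medians may become slightly shorter.
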